### 9 Subject selection

Patients will be enrolled at any time after 23.0 weeks gestation and prior to cesarean

### 9.1 Inclusion criteria

- 1. Scheduled/non-labor or unscheduled/labor cesarean delivery
- 2. Gestational age  $\geq$  23 weeks

### 9.2 Exclusion criteria

- 1. Unwilling or unable to provide consent
- 2. Non-availability for postoperative follow-up
- 3. Contraindication to NPWT
  - Pre-existing infection around incision site
  - Bleeding disorder
  - Therapeutic anticoagulation
  - Allergy to any component of the dressing (e.g., silver, silicone, adhesive tape)
  - Prior irradiated skin

### 9.3 Withdrawal criteria and procedure

Patients will be withdrawn from the study for any of the following reasons:

- 1. Patient requests early discontinuation.
- 2. Patient undergoes removal of the study device
- 3. Patient is lost to follow up.

The patient can leave the investigation at any time, at the patient's request. The reason for withdrawal will be investigated and carefully documented in the Patient's Medical file and the appropriate section of the Case Report Form. When a patient withdraws or is withdrawn from the study, the final evaluation and the follow up will be performed as completely as possible. In addition, any comments (spontaneous or elicited) or complaints made by the patient or any other physician not related to the investigation but taking care of the patient

subsequently will be carefully recorded in the Patient's Medical File and related section of the Case Report Form.

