# 8.6 Primary Endpoint

Patient centered outcomes

- Patient satisfaction scores (scale of 0 10) at discharge and postoperative day 30 (+/- 2 days)
- Pain scores (scale of 0 10) at discharge, at removal and postoperative day 30 (+/-2 days)
- Patient satisfaction with aesthetic appearance (scale of 0 10) at postoperative day 30 (+/- 2 days)

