# 8.6.1 Secondary endpoints

Efficacy outcome

• Composite wound complication including wound infection, would separation, seroma, antibiotics prescribed for presumed SSI within 30 days (+/- 2 days)

Safety outcomes:

• Skin blistering, allergic reaction, wound bleeding

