# 10.4 Visit B: Post Procedure until Discharge

- Patients will be monitored daily while in the hospital by clinical staff and/or research staff for complications.
- The negative pressure wound therapy dressing will be removed on the day of discharge. If the patient remains hospitalized for more than 7 days, the dressing will be removed on postoperative day 7.
- Replacement of any dressing that is saturated.
- If a patient develops infection with the NPWT device in place the device will be removed and the patient given standard SSI therapy as outlined below.
- Patients will be educated about the signs and symptoms of infection and other study outcomes and encouraged to call their provider if these should arise.
- Research staff document inpatient course regarding SSI.
- Management of surgical site infections will follow the Practice Guidelines of the Infectious Diseases Society of America.

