### **10.6** Discontinuation of subjects

If a patient develops a wound complication the Principal Investigator or patient's provider will determine if the NPWT device should be discontinued.

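### Section 9.3 withdraws women from the study on device removal, planned or not; even if only early removal is meant, withdrawal is tied to the outcomes and no denominator is stated

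*Combined protocol and SAP*

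**What the plan says.** Section 9.3 gives three reasons for which a woman is to be withdrawn from the study. The second is "Patient undergoes removal of the study device". Item 1 speaks of early discontinuation; item 2 has no such limit. For anyone withdrawn, the same section adds that "the final evaluation and the follow up will be performed as completely as possible".

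Section 10.4 describes routine removal: "The negative pressure wound therapy dressing will be removed on the day of discharge", or on postoperative day 7 for a longer stay. It also says: "If a patient develops infection with the NPWT device in place the device will be removed". Section 10.6 is headed "Discontinuation of subjects", but its text concerns only the device: after a wound complication the investigator or provider "will determine if the NPWT device should be discontinued".

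Sections 8.6, 10.5 and 10.5.2 schedule pain, satisfaction and outcome assessments at day 30 and at 4 to 6 weeks, whatever the device status. Section 8.6 also asks for a pain score at removal itself. The secondary efficacy endpoint in section 8.6.1 is a "Composite wound complication including wound infection" among other events. The safety endpoints include skin blistering and wound bleeding.

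Section 15 promises proportions with 95% confidence intervals. It names no analysis set, no endpoint denominator and no rule for withdrawn women or missing scores.

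**The concern.** As written, item 2 withdraws every participant at a step that the protocol itself schedules for all of them, before most of the primary endpoint is measured.

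Reading it as early removal settles that conflict but leaves a second one. Early removal is compulsory for an infection that arises with the device in place and discretionary after a wound complication. Section 7.1 describes removal as all that most skin reactions in earlier series required. The women labelled withdrawn would therefore tend to be those who had the events that the study counts. Their day-30 pain and satisfaction scores would be collected on a best-effort basis, and an analyst could leave them out or keep them in without departing from section 15. A reader of the report could not tell which denominator had been planned.

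**Working it through.** There is no planned figure to reproduce: section 15.1 makes no formal sample size calculation. The check compares the passages and then sizes the denominator question.

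**Passages side by side**

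- Trigger (9.3): any removal of the device leads to withdrawal from the study.
- Routine course (10.4): every dressing is off by discharge or day 7. The wording there is dressing, not device, but no passage keeps the device on after the dressing is off.
- Later assessments (8.6, 10.5, 10.5.2): these are due at day 30 and at 4 to 6 weeks for everyone. They show that item 2 cannot have been meant literally.
- Early removal (10.4, 10.6): this follows infection or a wound complication, and 8.6.1 counts both as outcomes.
- Analysis (8.5, 15): 8.5 takes in all eligible women, and 15 describes the recruited group. Both lean towards keeping everyone, but neither sets an endpoint denominator.

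**How many women might be involved**

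Inputs: 30 women (sections 6 and 15.1); skin irritation or blisters in 10-15%, about 90% of these needing nothing beyond removal (7.1); SSI in up to 12% (section 5).

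- Skin reactions: 0.10 × 30 = 3.0 to 0.15 × 30 = 4.5.
- Of these, managed by removal alone: 0.9 × 3.0 = 2.7 to 0.9 × 4.5 = 4.05.
- SSI: at most 0.12 × 30 = 3.6.

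These are upper guides only. Section 7.1 describes other series and does not say that removal was early. Only infections arising with the device in place trigger removal.

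**Effect of leaving affected women out**

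With x affected women of 30 and k of them excluded, the proportion falls by x/30 − (x − k)/(30 − k).

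- k = 1, x = 1 to 6: 3.3, 3.2, 3.1, 3.0, 2.9, 2.8 percentage points.
- k = 2, x = 2 to 6: 6.7, 6.4, 6.2, 6.0, 5.7 percentage points.

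Example with an assumed 4 affected women and exact (Clopper-Pearson) 95% intervals:

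| Excluded | Result | 95% CI |
|---|---|---|
| 0 | 4/30 = 13.3% | 3.8 to 30.7 |
| 1 | 3/29 = 10.3% | 2.2 to 27.4 |
| 2 | 2/28 = 7.1% | 0.9 to 23.5 |
| 4 | 0/26 = 0% | 0 to 13.2 |

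If the four events were device related, the point estimate would move from above to below the 10% level in section 8.4 through the choice of denominator alone. That level is not a formal test, and the intervals overlap widely.

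**Scores**

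If 4 of 30 women were dropped and their mean score was d points worse than that of the rest, the overall mean would shift by (4/30) × d. This is 0.27 points for d = 2 and 0.53 for d = 4, on the 0 to 10 scale. The counts and differences are assumptions.

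**The case against.** The best case for the plan is that nothing need be lost. Section 9.3 continues follow-up after withdrawal, so even the literal reading does not cancel the later assessments. Section 10.5.1 abstracts charts through 6 weeks. An infection or blister that leads to removal has already happened and would be on record. No passage tells the analyst to exclude anyone. Every event and exclusion count above is assumed, and many SSIs may appear after routine removal and never engage item 2. Section 9.3 also already requires the reason for withdrawal to be documented. One qualifying word in item 2 and one sentence on denominators might seem enough.

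Most of this stands as a limit on size: the effect may be nil, and data collection is meant to go on. It does not remove the contradiction between 9.3 and 10.4, and it does not supply a denominator. Best-effort follow-up is weaker than a scheduled assessment, and this matters most for the day-30 scores, which charts cannot replace. Adding the word early would cure the conflict with 10.4 but would keep withdrawal tied to the outcomes. The denominator gap also affects women who leave at their own request or are lost to follow-up. Item 2 is the reason for withdrawal that the protocol itself links to the endpoints.

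**Conclusion.** The concern holds and should be fixed. A stated rule is wrong as written, and on its probable meaning it links withdrawal to infection and wound complications while section 15 leaves the denominators open. Confidence in the textual conflict is high.

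The consequence cannot be sized from the documents. It runs from none, if every withdrawn woman is kept, to roughly 3 percentage points for each affected woman left out of 30. This rests on assumed counts, and it arises only if withdrawn women are excluded. Bias is possible, not demonstrated.

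**What to change.** - Delete item 2 of section 9.3 and reconcile that section with 8.6, 10.4 and 10.6. State that removal of the device, planned or early, ends device use but not study participation, and that all scheduled assessments remain due.
- Retitle section 10.6 so that it refers to the device and not the subject.
- Record the date and reason of device removal separately from the date of study completion or withdrawal (section 13).
- In section 15, state that all women who received the device stay in the endpoint analyses whatever the time of removal. Give the number observed for each endpoint and say how missing day-30 scores are handled.
- Because enrolment is at consent (10.1), report as feasibility results the number enrolled but not fitted, out of all enrolled, and the number, timing and reasons of early removals.

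When and why the device comes off stays with the existing clinical passages. The cost is protocol wording, one case report form field and a few sentences in section 15; the calls and chart reviews are already scheduled. The downside is that complication rates may look slightly less favourable.

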# 9.4 Patient Identification and Confidentiality

Patients will be identified on all CRFs by a unique number. CRFs are confidential documents and will only be available to the sponsor (including sponsor delegates, like CRAs), the Investigator, the investigation statistician, and if requested to the advisory committee and regulatory authorities. The Principal Investigator for each centre will maintain as part of the investigation file a list identifying all patients entered into the trial.

# 10 Enrollment and Procedures

Patients will be enrolled at any time after 23.0 weeks gestation and prior to cesarean delivery. Enrollment activities may occur at prenatal appointments or upon admission to the Labor and Delivery unit. Each center will have the flexibility to use an approach that is most efficient and suitable for their system to screen and consent patients. Medical records of all potential patients will be reviewed and those who satisfy inclusion and exclusion criteria will be approached and written informed consent obtained. A screening log will be used to track all patients approached for the study (see Flow Chart below).

[figure not shown]
# 10.1 Enrollment

Patients will be considered enrolled in the study once they have provided documented consent. Consent from patients will be obtained in a private setting, such as a quiet conference area or the patient's private room. All subjects will be provided a copy of the signed informed consent form to take home. The informed consent process will be documented. There will be no randomization. All patients enrolled will receive the Medela INVIA Motion system.

# 10.2 Data collection

We will collect detailed antepartum, intrapartum, and postpartum information from study participants into a comprehensive database. Data will be collected and managed with *REDCap* (Research Electronic Data Capture), an established, secure, web-based data capture and management tool developed at Vanderbilt University and supported by the bioinformatics team at Indiana University School of Medicine

- Trained research staff in obstetric and perinatal outcomes abstraction will be responsible for all research data abstraction from patient records
- Research staff will undergo centralized specific training to ascertain study outcomes
- Standardized information will be abstracted from all charts regardless of study group
- Relevant data will be collected initially to assess eligibility. Complete baseline, outcome, wound culture, and cost data will be collected via direct interview and chart review
- Several data collection forms will be used during these processes, including forms for maternal baseline data, preoperative and intraoperative care, maternal outcomes, postpartum clinic/hospital outcomes

Data on these forms devoid of
 personal identifiers will be securely
 sent to the data management center through web-based entry

# **10.3 Visit A: Interventional Procedure**

All enrolled patients will receive the Medela INVIA Motion device placed by the patient's surgeon after the skin is closed with subcuticular suture or staples. Research staff and clinicians (labor & delivery and postpartum nurses, OR technicians, physicians, etc.) involved in the study will receive formal training on how to place and remove the prophylactic NPWT device.

# 10.4 Visit B: Post Procedure until Discharge

- Patients will be monitored daily while in the hospital by clinical staff and/or research staff for complications.
- The negative pressure wound therapy dressing will be removed on the day of discharge. If the patient remains hospitalized for more than 7 days, the dressing will be removed on postoperative day 7.
- Replacement of any dressing that is saturated.
- If a patient develops infection with the NPWT device in place the device will be removed and the patient given standard SSI therapy as outlined below.
- Patients will be educated about the signs and symptoms of infection and other study outcomes and encouraged to call their provider if these should arise.
- Research staff document inpatient course regarding SSI.
- Management of surgical site infections will follow the Practice Guidelines of the Infectious Diseases Society of America.

# **10.5 Visit C: Postpartum Follow Up**

We will use active surveillance by research staff to ascertain surgical site infections:

- Research staff will follow-up with the research participant at time of discharge or within 48 hours post discharge (postpartum day 1-9) to assess for adverse events, assess the participant's pain, obtain their satisfaction with their dressing and aesthetic appearance of the incision.
- A \$25 gift card will be disbursed to the participant.

Version 1.0: 15 November 2019

- Research staff will call subjects on approximately postoperative day 30 (±2 days). • They will ask the patient standardized questions regarding wound complications, patient satisfaction, pain and aesthetic appearance. If the patient reports a hospital, clinic, or ER visit not associated with the study centers, the staff will obtain the name of the medical facility and request the records.
- The EQ-5D-3L quality of life questionnaire will be administered at the 30-day call. •
- Medical records from postpartum clinic visits as well as records of unscheduled visits (to any hospital clinic or ER) will be sought to ascertain study outcomes.
- At the time of the subject's standard of care postpartum appointment about 4-6 weeks • after inpatient hospital discharge research staff will collect information on outcomes, pain and patient satisfaction. If the patient does not attend the clinical postpartum visit, the study staff will contact the subject by phone to collect the data. A \$50 gift card will be disbursed to the participant once this postpartum visit is complete.

### 10.5.1 Chart Abstraction

Data from the subject's prenatal record, delivery admission, and all clinic or hospital visits through the 6 week postpartum period, including medications and procedures will be collected.

# 10.5.2 Schedule of Events

|  | Enrollment | At Discharge or
Within 48 hours Post
Discharge (PP Day
1-9) | Post-Op Day
30 (+/- 2 days) | Post-Op ~4-6 Weeks
Postpartum Visit |
|--|------------|--|--------------------------------|--|
| Eligibility  | Х          |  |                                |  |
| Interview: Maternal Demographic
Characteristics | Х          |  |                                |  |
| Chart abstraction: Prenatal Records                |            | Х  |                                |  |
| Chart abstraction: Labor & Delivery                |            | Х  |                                |  |
| Patient Satisfaction Survey                        |            | Х  | Х                              | Х                                      |
| AE/SAE Form (if applicable)                        |            | Х  | Х                              | Х                                      |
| Chart abstraction: Outcome
Assessment           |            | Х  |                                | Х                                      |
| Disburse gift card                                 |            | Х  |                                | Х                                      |
| Chart abstraction: Postpartum                      |            |  |                                | Х                                      |

### **10.6** Discontinuation of subjects

If a patient develops a wound complication the Principal Investigator or patient's provider will determine if the NPWT device should be discontinued.

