# 8.5 Study design

This study will be a two center case series of women undergoing caesarean delivery conducted at two medical centers in Indianapolis, Indiana.

All patients meeting inclusion criteria will be included. All enrolled patients will receive the Medela INVIA Mation prophylactive NPWT device.

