### 15.1 Determination of Sample Size

As this is a feasibility study, no formal sample size estimation is performed. A sample of 30 will be sufficient to test feasibility and patient reported outcomes.

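### Sections 10.4 and 10.6 give two unreconciled rules for the device when a wound infection develops with it in place, and Section 9.3 lists device removal as a withdrawal reason without separating planned from early removal

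*Combined protocol and SAP*

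**What the plan says.** Four sections of the protocol bear on the point.

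- **Section 10.4 (Visit B)**, on infection: "If a patient develops infection with the NPWT device in place the device will be removed", followed by standard treatment for surgical site infection (SSI). The wording is mandatory.
- **Section 10.6 (Discontinuation of subjects)**, on a wound complication of any kind: "the Principal Investigator or patient's provider will determine if the NPWT device should be discontinued". The wording is discretionary and names who decides.
- **Section 8.6.1 (Secondary endpoints)** defines the efficacy outcome as "Composite wound complication including wound infection", together with separation, seroma and antibiotics given for presumed SSI, within 30 days.
- **Section 9.3 (Withdrawal criteria and procedure)** lists "Patient undergoes removal of the study device" as a reason for withdrawal. It adds that after withdrawal "the final evaluation and the follow up will be performed as completely as possible".

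Section 10.4 also sets the planned removal for everyone: "The negative pressure wound therapy dressing will be removed on the day of discharge", or on postoperative day 7 for a woman still in hospital.

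**The concern.** A woman whose incision becomes infected while the device is on meets the condition in 10.4 and also the condition in 10.6. One section settles what happens to the device; the other leaves it to a clinician's judgement. Staff who consult only 10.6, which is the section headed for discontinuation, would not learn that a mandatory rule exists elsewhere.

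Three things depend on this.

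- **Handling of a safety event.** Two clinicians could follow the protocol in good faith and treat the same event differently.
- **Deviation reporting.** Section 11.2 requires every deviation to be recorded, and those that may compromise patient safety to be reported to the IRB. Section 14 has monitors check conduct against the plan. Neither can be done consistently while two sections disagree about what compliance is.
- **Participant status.** Section 9.3 ties withdrawal to device removal, and Section 15 does not say how withdrawn women are analysed or which denominator applies.

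**Working it through.** The plan states no figure on this point, so there is none to reproduce. The check is mainly a comparison of text, with a short calculation for scale.

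**Step 1. Do the two rules cover the same event?** The condition in 10.4 is infection with the device in place, and its reference to SSI therapy shows that an infection of the wound is meant. The condition in 10.6 is a wound complication. Section 8.6.1 names wound infection first among the wound complications. Section 10.6 has no carve-out for infection and does not refer to 10.4. The overlap is therefore wound infection while the device is on.

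**Step 2. Do they give the same instruction there?**

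| Action after a wound infection with the device on | Under 10.4 | Under 10.6 |
|---|---|---|
| Device removed | Complies | Complies, if the investigator or provider so determines |
| Device left in place by clinical decision | Deviates | Complies |

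The sections agree in the first row and disagree in the second. No section states precedence.

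**Step 3. What does 9.3 add?** Its second withdrawal reason has no qualifier such as early or unplanned. Section 10.4 removes every dressing by discharge or day 7. If removing the dressing at that point counts as removing the study device, the literal result is that all 30 women are withdrawn before day 30. This cannot be intended: Section 8.6 schedules a pain score at removal, and pain, satisfaction and aesthetic scores at day 30, as primary endpoints for the whole series. If early removal is what is meant, 9.3 needs to say so. Under the literal reading, the conflict between 10.4 and 10.6 changes only the date of withdrawal. Under the early-removal reading, it can change whether an infected woman is classed as withdrawn.

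**Step 4. How many women might be affected?** Inputs:

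- n = 30 (Section 15.1: "A sample of 30 will be sufficient to test feasibility and patient reported outcomes").
- p = 0.12, the upper background SSI rate after cesarean cited in Section 5.
- s, the share of infections that arise while the device is on. The documents do not give s, so it is assumed.

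Expected infections = n × p = 30 × 0.12 = 3.6.

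Expected women under both rules = n × p × s. The chance of at least one = 1 − (1 − p × s)^30, taking women as independent with equal risk.

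| Assumed s | p × s | Expected women | Chance of at least one |
|---|---|---|---|
| 10% | 0.012 | 0.36 | 30.4% |
| 25% | 0.030 | 0.90 | 59.9% |
| 50% | 0.060 | 1.80 | 84.4% |
| 100% (ceiling) | 0.120 | 3.60 | 97.8% |

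Because 12% is itself an upper figure, these counts lean high.

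**The case against.** The strongest reply is that this is ambiguity rather than contradiction. Section 10.4 is a specific rule for infection, and 10.6 is a general rule that also covers separation and seroma. On the usual principle that the specific governs the general, a site that follows 10.4 for infection breaches nothing in 10.6. That reading is plausible, and Step 2 confirms that the sections can both be satisfied. But the protocol does not state it, and a clinician who relied on 10.6 to leave the device on would be within that section's wording. The objection reduces the seriousness of the conflict and does not remove it.

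A second reply concerns consequences, and most of it stands.

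- A reader might infer that the choice of rule decides who remains in the study. The documents do not support that. Section 9.3 continues evaluation and follow-up after withdrawal, Section 10.5 provides the day-30 call and active surveillance, and Section 10.5.1 continues chart abstraction to 6 weeks.
- A reader might infer that each affected woman shifts the reported proportions. The composite in 8.6.1 has no exclusion for device removal, so as written the event counts under either rule. A shift would need withdrawn women to be dropped, and no section says that they are.
- A reader might infer that different handling at the two sites confounds a comparison between them. Section 15 plans subgroup summaries by site in a descriptive series, with no between-site hypothesis or test.

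What remains open on the analysis side is narrower: Section 15 is silent on withdrawn women, and those affected here would by definition have had a secondary-endpoint event.

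**Conclusion.** The point holds as an internal inconsistency. For a wound infection with the device in place, 10.4 mandates removal, 10.6 leaves it to clinical discretion, and precedence is not stated. One permitted course under 10.6 is a deviation under 10.4. Section 9.3 compounds this by making device removal a withdrawal reason in terms that, read literally, cover the planned removal of every woman.

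The numbers are small and uncertain: 0.36 to 1.8 women of 30, if the cited 12% rate applies and 10% to 50% of infections arise while the device is on. The share is an assumption, and the documents cannot narrow it. The case for changing the text rests on consistent handling and reporting of a safety event and on a clear participant status. It does not rest on a demonstrated bias in any estimate. Which clinical rule should apply is not a question for this review.

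**What to change.** 1. Reconcile Sections 10.4 and 10.6 so that a single passage states how the device is handled when an infection or another wound complication occurs, and have the other section refer to it. The clinical team decides the content of the rule.
2. Amend Section 9.3 so that device removal, planned or early, ends device use only and is not in itself a reason for withdrawal from the study.
3. State in Sections 9.3 and 15 that a woman whose device is removed stays in the analysis and in all scheduled follow-up (the day-30 call, the 4-6 week postpartum visit and chart abstraction through 6 weeks), and that her wound complication counts in the composite.

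The cost is a wording amendment, which Section 11.1 requires to be submitted to the IRB for approval before it takes effect. It needs no additional patients, visits or data.
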